Upper airway purge is important to alveolar gas exchange as the gas that is drawn to the respiratory regions of the lungs comes from the dead space or anatomical reservoir created by the flush, in the same way that oxygen conservation masks (re-breathers) can incorporate reservoir bags to reduce the bulk flow requirements from the oxygen source to achieve the same oxygenation effect.  Based on mathematical modeling, physiologic studies and clinical observations, a flow rate of 4 to 8 L·min through Vapotherm's neonatal cannulae, or 25 to 40 L·min through Vapotherm's adult cannulae, would purge the anatomical reservoir of the upper airway in the window of time between breaths. 

Vapotherm's humidification system is specifically designed to tolerate a high back pressure in the humidification cartridge that is generated by passing these flow rates through small bore cannulae that result in the appropriate flow velocities (turbulent energy).  Since 2000, Vapotherm HVNI has been used extensively and has been well studied and the clinical impact of this ventilation effect using Vapotherm's conventional cannula line is well described  A multi-center recent randomized clinical trial also demonstrated the noninferiority of HVNI to NIPPV in the treatment of undifferentiated respiratory distress for patients presenting to the Emergency Department.  As Vapotherm leads the innovation of new cannulae for the purpose of HVNI, we seek to evaluate the ability of these cannulae to impact ventilatory work effort on dyspneic patients. The goals of the current study are to: (1) evaluate if next generation dual prong (Prosoft) cannulae provide comparable dyspneic relief among hypercapnic adults with accompanying dyspnea compared to current legacy (control) cannula design, and (2) assess if next generation Solo (Unicorn) cannulas at lower flows provide comparable dyspneic relief among hypercapnic adults with accompanying dyspnea compared to current legacy to Dual-prong cannula (Prosoft) design.

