## **II. Overall Study Objective**

The **overall objective** of this study is to evaluate the ability of HVNI next generation Prosoft nasal cannula designs to effect ventilation and related physiological responses relative to the conventional legacy cannula design, with which there are published clinical outcomes data.

The **hypothesis**: The next generation nasal cannula designs (Prosoft and Unicorn) will be comparable at relieving patient dyspnea while on HVNI, when compared to the conventional legacy cannula.

To test this hypothesis, the study will be conducted with the following specific aims:

Aim #1: Primary Outcome. The primary endpoint is the patient's targeted relief of dyspnea, as measured by the modified Borg scale (rated perceived dyspnea [RPD]) for each cannula design tested.

Aim #2: Secondary Outcomes. The secondary endpoints evaluate the patient vital signs (heart rate [HR], respiratory rate [RR], blood pressure [BP]), arterial oxygen saturation (SpO2), and arterial CO2 as measured by a transcutaneous CO2 device (TcPCO2). These measurements will be compiled for each cannula design tested.

Aim #3: Tertiary Outcomes. The tertiary endpoints evaluate both patient and clinician perception assessment scores. For patient perception/satisfaction these endpoints include: (1) relief of symptoms, and (2) comfort/tolerance. For clinician perceptions these endpoints include: (1) technical/clinical difficulties, (2) patient comfort & tolerance, (3) ease of use, (4) monitoring & support for therapy, and (5) expected/perceived patient outcomes.

These **endpoints** will establish equivalence of outcomes between the legacy cannula and the new cannula designs (both Unicorn and Prosoft) in terms of the ability to relieve dyspnea in adult hypercapnic patients experiencing dyspnea.

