## Sample Size:

To provide a sufficiently powered sample dataset, we will enroll up to 32 subjects to complete this study on nasal cannula designs, with a calculated sample size of N=26 plus a 20% failure/fallout rate. This will provide sufficient data to adequately inform on the study objectives.

This sample size was estimated through use of references that (1) approximated minimal clinical important difference of dyspnea (modified Borg scale) and (2) approximated expected standard deviation of prior datasets measuring dyspnea. Estimated minimal clinical important difference of dyspnea was determined to be a difference value of 2 in modified Borg for dyspnea. In reviewing publications from Roca 2010 and Schwabbauer 2014, it was estimated that a value of 2 to 3 was suitable for the standard deviation of dyspnea for the modified Borg scale. Therefore, for this study, using the paired t-test sample size calculation, with an expected difference of 2, and an expected standard deviation of 3, using a desired power of 90% with alpha=0.05, the sample size is estimated at 26 to show if the data may or may not have any difference.

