## VII. Data Collection

## Table 1. Key study data and collection points for each Phase of the Study.

	Baseline Characterization	Therapy Acclimatization	Therapeutic Characterization	@ Study End
Patient History & Health	Х			
Treatment: Flow & O2	Х	Х	Х	
Physiologic Parameters	Х	Х	Х	
Ventilation Parameters	Х	Х	Х	
Clinician Perception Scores			X	Х
Patient Perception Scores			Х	Х

Patient enrollment data collection will include patient history, health, demographics, and current respiratory therapies. Only Phase 1 will record the patients' history and background information. For each segment of each phase, the following data will be recorded for comparison:

Physiologic Parameters o SpO2, HR, RR, BP Ventilation Parameters o RPD, TcPCO2

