## VIII. Statistical Analysis

The data analysis will be "per protocol." Baseline patient demographics and characteristics will be summarized, compared, and appropriate statistical testing will be performed for the continuous and categorical variables. Assuming a non-normal data distribution for this crossover order-randomized study design, the non-parametric Wilcoxon Signed Rank Sum test will be performed with significance interval of 0.05 on all applicable variables. Parametric analytical analogues (e.g. t-test) will be use if the measurements present a normal distribution. Otherwise, for the categorical variables, the Fisher's Exact test will be performed. Data will be compared and graphed accordingly for a visual comparison with accompanied statistical notations.

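### Section VIII tests every variable at an unadjusted 0.05, and the document does not fix which cannula contrasts on dyspnea decide the study

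*Combined protocol and SAP*

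**What the plan says.** Section VIII is the whole analysis plan. Its operative sentence is that "the non-parametric Wilcoxon Signed Rank Sum test will be performed with significance interval of 0.05 on all applicable variables". Paired t-tests replace the rank test where data look normal, and Fisher's exact test is used for categorical variables. The section gives no list of contrasts, no order of testing, no multiplicity rule and no analysis time point.

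The endpoint hierarchy is stated elsewhere. In Section II, "The primary endpoint is the patient's targeted relief of dyspnea, as measured by the modified Borg scale", and Section VII labels the physiologic readings and TcPCO2 secondary and the patient and clinician VAS scores tertiary.

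The contrasts are stated differently in different places:

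- **Section II, overall objective:** names Prosoft only, against legacy.
- **Section II, hypothesis:** names both Prosoft and Unicorn, against legacy.
- **Section II, closing sentence:** says that the endpoints "will establish equivalence of outcomes between the legacy cannula and the new cannula designs (both Unicorn and Prosoft"; after the bracket, it limits the claim to relief of dyspnea.
- **Section I, goal 2:** describes Unicorn as "compared to current legacy to Dual-prong cannula (Prosoft) design", which can be read as legacy, Prosoft or both.
- **Section IV:** sets both new designs against legacy.

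On timing, Section VII says: "For each segment of each phase, the following data will be recorded for comparison". Section IV says that primary and secondary outcomes are completed at the end of each phase. The Phase 2 procedures, which also apply to Phase 3, add a repeat reading when settings are changed.

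**The concern.** The 0.05 in Section VIII is an error rate per test. It would be the error rate of the trial's conclusion only if one test carried that conclusion. Here the primary variable is fixed, but its contrast and reading are not, and the same 0.05 is applied to every other variable.

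Two things are at stake. First, the trial sets out to show comparability. If the cannulas really are the same, unadjusted difference tests on many variables can produce a nominally significant result that contradicts the intended conclusion, and the plan does not say how to weigh it. Second, the study is not blinded and the contrasts are open, so a chance result favouring a new cannula could be selected and reported as a finding.

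**Working it through.** **1. The plan's own figure.** Section V bases the size of the trial on a single paired t-test. Its inputs are given as "with an expected difference of 2, and an expected standard deviation of 3, using a desired power of 90% with alpha=0.05". Taking 3 as the SD of the paired difference and a two-sided test, the noncentrality at n = 26 is (2/3) × √26 = 3.40. Exact noncentral-t power is 90.4%, so N = 26 reproduces. Adding 20% gives 26 × 1.2 = 31.2, rounded up to the stated 32. The calculation covers one contrast on one variable and does not say which contrast.

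**2. Number of variables** (Sections II, VI and VII).

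- Primary: RPD, 1.
- Secondary: SpO2, HR, RR, BP and TcPCO2, 5, or 6 if systolic and diastolic BP are tested separately.
- Tertiary: 2 patient and 5 clinician VAS scores, 7.
- Total: 1 + 5 + 7 = 13, or 14 with BP split.

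**3. Number of tests, one reading per phase.** Two contrasts (each new design against legacy) give 26–28 tests. A third (Unicorn against Prosoft) gives 39–42. With identical cannulas the expected number of p-values below 0.05 is 0.05 × 28 = 1.4 or 0.05 × 42 = 2.1 at the upper counts. This expectation does not depend on correlation.

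**4. RPD alone.** Independent tests would give 1 − 0.95² = 9.75% and 1 − 0.95³ = 14.3%. The contrasts share cannula data, so I simulated three identical cannula means, formed z = (difference)/√2 for each pair and counted any |z| > 1.96. The result is 9.1% for two contrasts and 12.3% for three.

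**5. All variables.** The simulation was the same, with 13 or 14 variables sharing a common correlation ρ. The documents give no value for ρ, so it is an assumption, shown over a range. The table gives the chance of at least one p < 0.05; each range runs from 13 to 14 variables.

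| ρ | Two contrasts | Three contrasts |
|---|---|---|
| 0 | 71–74% | 82–84% |
| 0.3 | 63–66% | 74–76% |
| 0.5 | 53–54% | 63–65% |
| 0.7 | 40–41% | 49–50% |
| 0.9 | 24% | 30–31% |

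A separate simulation of the signed-rank test itself at n = 26 (4,000 replicates per setting) agrees within about 5 points. At ρ = 0.5 it gives 54–56% and 66–68%; at ρ = 0.9 it gives 26–27% and 34–35%.

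Testing more than one segment per phase would raise all of these figures.

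**The case against.** The strongest reply is that these figures measure the less dangerous error. The trial wants to conclude comparability, so a chance difference mostly counts against the sponsor. The graver risk is to read a non-significant difference test as equivalence when no margin is stated. If both designs had to meet a margin, no alpha split between them would be needed. This stands, and it shapes the fix. It does not rescue Section VIII, which states neither a margin nor such a rule.

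Second, a reader might infer from the plural 'endpoints' in Section II that all three tiers carry the conclusion and that the sponsor may pick any endpoint. The documents do not support that. RPD is the one named primary endpoint, the others are labelled secondary and tertiary, and the Section II sentence is limited to relieving dyspnea. What remains open for RPD is the contrast and the reading.

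Third, two contrasts against legacy is the best-supported reading, given the hypothesis, the closing sentence of Section II and Section IV. The three-contrast figures rest on one garbled phrase in Section I. That is fair, and the two-contrast figures should be given more weight.

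Fourth, unadjusted tests on secondary and tertiary variables are often accepted as exploratory in a study of this size. True, but Section VIII does not label them so.

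**Conclusion.** The point holds as a gap in the analysis plan. On RPD, leaving the contrast open raises the chance of a false difference from 5% to about 9% (two contrasts) or 12% (three). Over all variables the chance of at least one is about 53–74% or 63–84% for an assumed correlation of 0.5 to 0, and about 24–31% at 0.9. These figures assume identical cannulas, one reading per phase, 13 or 14 variables and a common correlation.

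A reader might go further and say that identical cannulas would probably show a significant difference somewhere. That depends on a correlation of roughly 0.5 or less for two contrasts, and somewhat under 0.7 for three. The documents give no correlation, and some scores overlap closely, such as the patient's and the clinician's ratings of patient comfort. Nor does the inflation make a false claim of equivalence easier; it mostly works the other way. The sample-size arithmetic is sound for the single comparison that it covers.

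**What to change.** 1. **State one set of contrasts.** In Sections I, II and VIII, name the same RPD contrasts: Prosoft against legacy, and Unicorn against one named comparator. Legacy is the comparator best supported by Sections II and IV. Name the one reading per phase that is analysed, say how a repeat reading after a settings change is handled, and state that RPD alone carries the conclusion.
2. **Judge those contrasts against a margin.** Use paired estimates with confidence intervals and a pre-stated equivalence margin. If both designs must meet it, no alpha split is needed. If each design may be claimed separately, use a fixed order in which meeting the margin opens the next step. A gate based on a significant difference would reverse the aim, since Unicorn would be tested only if Prosoft differed from legacy. A gate based on non-significance would control no error.
3. **Report secondary and tertiary variables as exploratory.** Give paired estimates with 95% intervals, without significance claims.

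The contrast and reporting changes are wording only. The sponsor gives up significance claims on secondary and tertiary variables and has to choose and justify a margin, after which N = 26 should be checked against it. Keeping difference tests with a Bonferroni split instead would cost more. Two RPD contrasts at 0.025 need 31 evaluable patients, and power at 26 falls to 83.8%; three at 0.0167 need 34, and power at 26 falls to 79.1%. That route would still not address the equivalence aim.

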## IX. Risks and Discomforts

This study does not present significant risk to patients, as supplemental oxygen is routinely provided to patients as a means of standard/routine practice in the study hospitals . Use of high flow nasal cannula therapy has no known risks and has been used in the clinical setting for approximately 17 years without known reports of adverse events related to the administration of high nasal flows when appropriately conditioned to near body temperature and fully humidified. The literature indicates that approximately only 4 cmH2O of distending pressure may be generated in the upper airway, which is well below any known threshold for injury.  Additionally, it has been demonstrated that delivery of high flows of conditioned gas from a nasal cannula has a positive effect on airway mucosal function.  The patients will be closely monitored as part of standard medical practice.

For these reasons, we have determined that this study represents non-significant risk to the subjects. The high flow nasal cannula system used has no known risk and has been used in hospitals for about 17 years. During both sessions, patients will be closely monitored as part of the normal care. Patients may experience mild discomfort from a cannula coming into contact with their nose, face or around their ears; patients may also experience runny nose from the humidity contained in the gas flow.

## X. Potential Benefits

Subjects may or may not receive any direct health benefit from participation. Due to the short duration of the exposure, it is not likely that the patients enrolled in the HVNI cannula study will themselves benefit from participation in this study. The trial may result in scientific knowledge that leads to improvements in the quality of patient care, patient experience, and the effect cannula designs have on patient dyspnea relief.

## HVNI Cannula Efficacy in Relieving Dyspnea

Confidential

## XI. Monitoring and Quality Assurance

The clinical trial site will be monitored in accordance with policies at Vapotherm and federal regulations that pertain to clinical research, namely 21 CFR Parts 50, 54, 56 and 812 and others as applicable. Monitoring will occur at regular frequency by the PI or designee, such as to allow ongoing review of data collected, site qualifications and compliance with the protocol. All investigators will be appropriately trained to ensure compliance with the protocol. Audits of the study CRF's will be regularly conducted by the Sponsor.

## **XII. Protocol Deviations**

Any deviations from the Data Collection plan identified during monitoring or through other means will be documented on case report forms. These include, but are not limited to items such as the following:

- Deviation from the procedural sequencing, per the protocol
- Failure to complete the Baseline characterization
- Failure to complete all sections of the Study Phases
- Failure to capture time and place in trial of any device failure
- Failure to capture/record data included in the protocol
- Subject inability to complete both the control and test study arms

If the study site demonstrates a pattern of consistent and frequent deviations, the sponsor will undertake appropriate activities (e.g. re-training) to attempt to bring the site into compliance with the protocol. A pattern of repeated serious deviations from the protocol may result in site termination from the study.

## XIII. Adverse Event Reporting

During the course of the subjects' participation in the study, the investigator will determine whether any adverse events have occurred. For the purposes of this protocol, an adverse event is defined as any undesirable event experienced by a subject, that is or is not attributed to the device or procedure required by this protocol. If any adverse event occurs, whether anticipated or unanticipated, the investigators will immediately contact the sponsor representative (site monitor) indicated on page 1.

## **XIV. Confidentiality**

Rigorous procedures will be followed to maintain confidentiality of subject identification and test-related information and to adhere to government regulations concerning privacy. Methods to protect the privacy of subjects and clinical information are employed and built into the trial. A unique identification number designed to protect the identity of subjects will be used to identify the subject on case report forms, recruitment logs, data forms or other reports.

This unique identification number will not be linked to identifiable data; no personal or identifiable patient data will be collected. The Vapotherm clinical research staff member managing the study will be the only person to have knowledge pertaining to the link between the unique identifiable number and the subject. All other Vapotherm representatives involved in this study will only have access to the patients' unique identification number. The linked data will be maintained by the site study staff and stored at the study site for two years from the end of the study.

## HVNI Cannula Efficacy in Relieving Dyspnea

Confidential

Confidentiality will be protected and maintained to the extent allowed by law.

